### 8.2. Efficacy Analysis

Censoring rules for time-to-event endpoints are detailed in [Section 11.3 Appendix 3](#).

### 8.3. Pharmacokinetics

#### Concentrations below the limit of quantification

In all data presentations (except listings), concentrations below the limit of quantification (BLQ) will be set to zero. (In listings BLQ values will be reported as “<LLQ”, where LLQ will be replaced with the value for the lower limit of quantification).

### **Deviations, missing concentrations and anomalous values**

In summary tables and plots of median profiles, statistics will be calculated with concentrations set to missing if one of the following cases is true:

1. A concentration has been reported as ND (ie, not done) or NS (ie, no sample).
2. A deviation in sampling time is of sufficient concern or a concentration has been flagged anomalous by the pharmacokineticist.

Note that summary statistics will not be presented at a particular time point if more than 50% of the data are missing.

### **Pharmacokinetic parameters**

Actual PK sampling times will be used in the derivation of PK parameters.

If a PK parameter cannot be derived from a subject's concentration data, the parameter will be coded as NC (ie, not calculated). (Note that NC values will not be generated beyond the day that a subject discontinues).

In summary tables, statistics will not be presented for a particular treatment group if more than 50% of the data are NC. For statistical analyses, PK parameters coded as NC will also be set to missing.

If an individual subject has a known biased estimate of a PK parameter (due for example to an unexpected event such as vomiting before all the drug is absorbed in the body), this will be footnoted in summary tables and will not be included in the calculation of summary statistics or statistical analyses.

### **QTc**

For the QTc analyses, no values will be imputed for missing data.

CCI [REDACTED]

[REDACTED]

## **9. STATISTICAL METHODOLOGY AND STATISTICAL ANALYSES**

### **9.1. Statistical Methods**

No formal hypothesis testing will be performed in this exploratory study.

### **Analyses of Time-to-Event Endpoints**

Time-to-event endpoints will be summarized using the Kaplan-Meier method and displayed graphically when appropriate. Median event times and 2-sided 95% confidence intervals for each time-to-event endpoint (Brookmeyer and Crowley, 1982) will be provided.

## **Analyses of Binary Endpoint**

The rates of binary endpoints will be provided along with the corresponding 2-sided 95% confidence intervals using an exact method.

## **Analyses of Continuous Data**

Descriptive statistics, such as the mean, standard deviation, coefficient of variation, median, minimum, and maximum values, will be provided for continuous endpoints.

### **9.2. Statistical Analyses**

#### **9.2.1. Primary Analysis**

Dose Limiting Toxicity (DLT) is the primary endpoint of the dose escalation component of the study, which will be summarized by dose level using the Safety Analysis Set for patients in the dose escalation portion of the study. A listing of the DLTs will also be provided.

If necessary, a summary and listing of the DLT may be provided using the Per Protocol Analysis Set for patients in the MTD expansion portion of the study.

#### **9.2.2. Secondary Analyses**

##### **9.2.2.1. Efficacy Analysis**

In this Phase 1 study efficacy is a secondary objective. Note that the efficacy analysis is to be conducted for patients in the MTD expansion cohorts who are in the Safety Analysis Set and have baseline disease assessment and at least one post-baseline disease assessment. In the event that a large number of patients in the escalation portion of the study have the same malignancy, the efficacy analysis may be conducted.

Summary tables of best Overall Response Rate, Progression Free Survival, and Overall Survival will be provided overall and by malignancy if necessary. Efficacy listings will be provided that include best response, first CR/PR date, last date with CR or PR, most recent date without progression, progression date, death date, date of first response and last tumor assessment date, etc.

A response rate overall for Part 1 dose escalation and response rates by low, medium, and high dose groups may be presented.

The following table provides an overview of the efficacy analysis.

Endpoint	Analysis Set	Statistical Method	Model/ Covariates/ Strata*	Missing Data	Interpretation
Overall response	Per Protocol, expansion cohorts, etc.	Exact CI	By dose range/ malignancy	Censored per Section 11.3	Secondary Analysis
Progression Free Survival (PFS)	Per Protocol, expansion cohorts	Kaplan-Meier	By malignancy	Censored per Section 11.3	Secondary Analysis
Time to Progression (TTP)	Per Protocol, expansion cohorts	Kaplan-Meier	By malignancy	Censored per Section 11.3	Secondary Analysis
Duration of Response (DR)	Per Protocol, expansion cohorts	Kaplan-Meier	By malignancy	Censored per Section 11.3	Secondary Analysis

\* If patients in dose escalation phase are included.

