2.2. Endpoints

Primary Endpoint (Part 1)

- First cycle Dose Limiting Toxicities (DLTs) in order to determine the MTD and RP2D.

Primary Endpoint (Part 2)

- Response rate (RR) as determined by the Response Evaluation Criteria in Solid Tumor (RECIST) version 1.1 criteria.

Secondary Endpoints

- Adverse Events (AEs) as characterized by type, frequency, severity (as graded by NCI CTCAE v.4.03), timing, seriousness and relationship to study treatment.
- Laboratory abnormalities as characterized by type, frequency, severity (as graded by NCI CTCAE v. 4.03) and timing.
- Vital Signs.
- Systemic pharmacokinetic (PK) exposure of ADC (PF-06650808), total antibody (PF-06460005) and unconjugated payload (PF-06380101) will be determined with validated methods. Standard noncompartmental PK parameters will be determined from the respective concentration-time data.
- Immunogenicity of ADC (PF-06650808); Human serum ADA (anti-PF-06650808 antibody) samples will be analyzed for the presence or absence of anti-PF-06650808 antibodies, following a tiered approach using screening, confirmation and titer/quantitation.
- Objective tumor response, as assessed using the Response Evaluation Criteria in Solid Tumor (RECIST) version 1.1 by calculating the Overall Response Rate (ORR), Progression Free Survival (PFS), and Overall Survival (OS) – Part 2 only.

CCI [REDACTED]

- CCI [REDACTED]
- CCI [REDACTED]
- CCI [REDACTED].
- CCI [REDACTED]

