9.4.1. Analysis of Overall Response

For patients to be considered evaluable for efficacy they must have received at least one dose of study medication and have a baseline tumor assessment. Patients must also present with measureable disease.

The best overall response is the best response recorded from first dose until disease progression/recurrence (taking as reference for PD the smallest measurements recorded since screening). In general, the patient's best response assignment will depend on the achievement of both measurement and confirmation criteria. All measurements (or "too small to measure") must be provided for every target lesion to document SD or PR.

The main goal of confirmation of objective response is to avoid an incorrect estimation of the response rate observed. In cases where confirmation of response is not feasible, it should be made clear when reporting the outcome of such studies that the responses are not confirmed.

To be assigned a status of PR or CR, changes in tumor measurements must be confirmed by repeat assessments that should be performed no less than 4 weeks after the criteria for response are first met. Clinical benefit response (CBR) is defined as a CR, PR or SD ≥ 6 cycles.

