## 7. ENDPOINTS AND COVARIATES

### 7.1. Efficacy Endpoint(s)

*Objective tumor response, as assessed using the Response Evaluation Criteria in Solid Tumor (RECIST) version 1.1 by calculating the Overall Response Rate (ORR), Progression Free Survival (PFS), and Overall Survival (OS).*

All efficacy endpoints are secondary in this study, which include objective tumor response, progression-free survival (PFS), and overall survival (OS) in the expansion cohort. The above efficacy endpoints are derived based on the disease response per investigator evaluation on the CRF pages, which is the primary method of documentation of disease.

- **Overall Response (OR)** – is defined as confirmed complete response (CR) or confirmed partial response (PR) according to RECIST 1.1 ([Appendix 2](#)). Confirmed responses are those that persist on repeat imaging study at least 4 weeks after the initial documentation of response. Patients who do not have on-study radiographic tumor re-evaluation, who receive anti-tumor treatment other than the study medication prior to reaching a CR or PR, or who die, progress, or drop out for any reason prior to reaching a CR or PR will not

be counted as responders in the assessment of OR. Clinical benefit response (CBR) is defined as a CR, PR or SD  $\geq 6$  cycles.

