## 7.2. Safety Endpoints

### 7.2.1. DLT Definition

Dose limiting toxicity (DLT) is the primary endpoint of this study. Severity of adverse events will be graded according to CTCAE version 4.03. For the purpose of dose escalation, any of the following adverse events which are not considered related to disease progression occurring in the first cycle of treatment (21 days) will be classified as DLTs:

- *Hematologic:*
  - *Grade 4 neutropenia lasting  $>7$  days.*
  - *Febrile neutropenia (defined as neutropenia  $\geq$  Grade 3 and a single body temperature  $>38.3^{\circ}\text{C}$  or a sustained temperature of  $\geq 38^{\circ}\text{C}$  for more than one hour).*
  - *Grade  $\geq 3$  neutropenia with infection.*
  - *Thrombocytopenia (of any grade) associated with clinically significant or life-threatening bleeding.*

- *Grade 4 thrombocytopenia  $\geq 72$  hours or platelets  $\leq 10,000/mm^3$  regardless of duration.*
- *Non-hematologic:*
  - *Grade  $\geq 3$  toxicities, except those that have not been maximally treated (eg, nausea, vomiting, diarrhea).*
  - *Delay by more than 2 weeks in receiving the next scheduled cycle due to persisting toxicities not attributable to disease progression.*

*In addition, clinically important or persistent toxicities that are not included in the above criteria may be considered a DLT following review by the sponsor and the investigators.*

*Grade  $\geq 3$  cytokine release syndrome, infusion reaction, and allergic reaction will not be considered as DLTs but may be a reason for study discontinuation and should be reviewed with the sponsor.*

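### Response rate is primary for Part 2 in the protocol but secondary in the SAP, and the SAP 9.2.2.1 denominator drops patients who can only be non-responders

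*SAP*

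**What the plan says.** **Status of the endpoint.** Protocol 2.2 gives the Part 2 primary endpoint as "Response rate (RR) as determined by the Response Evaluation Criteria in Solid Tumor (RECIST) version 1.1 criteria". The same section lists overall response rate again among the secondary endpoints, for Part 2 only. SAP 7.1 states "All efficacy endpoints are secondary in this study" and SAP 7.2.1 states "Dose limiting toxicity (DLT) is the primary endpoint of this study". SAP 9.2.1, the primary analysis, contains no Part 2 response analysis, and the table in SAP 9.2.2.1 labels overall response as secondary. Yet SAP 2.3 reproduces the Part 2 primary objective, which includes anti-tumor activity.

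**Who is counted.**
- Protocol 9.4.1: to be evaluable for efficacy "they must have received at least one dose of study medication and have a baseline tumor assessment", and have measurable disease. Nothing is required after baseline.
- SAP 9.2.2.1, text: expansion patients "who are in the Safety Analysis Set and have baseline disease assessment and at least one post-baseline disease assessment".
- SAP 9.2.2.1, table: "Per Protocol, expansion cohorts, etc", with missing response data referred to the censoring rules of Appendix 3.
- SAP 6.2 (same wording in Protocol 9.1): for the Per Protocol set, describes a baseline and a post-baseline assessment as suitable for efficacy analysis.
- SAP 7.1: "Patients who do not have on-study radiographic tumor re-evaluation" are among those who are not counted as responders.
- SAP 6.6.1: the modified ITT set keeps patients who progress or die before the first assessment. The use it mentions is presentation while the study is ongoing.

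**The concern.** Part 2 exists partly to estimate the response rate in this population (Protocol 3.1), and SAP 4.1 puts the emphasis on estimation. The Part 2 primary endpoint therefore needs one status, one analysis set and one missing-data rule. It has none of these, in an open-label study with investigator-assessed response.

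The SAP 7.1 non-responder rule does nothing for unassessed patients if 9.2.2.1 has already removed them. Those removed would mainly be early deaths and early withdrawals, so the restriction is related to outcome. A presentation during the study that used the modified ITT set could rest on a stricter denominator than the final analysis. Referring missing data to censoring rules has no meaning for a binary response.

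**Working it through.** **1. The plan's own figure.** The only figure given is the sample size: 35 (Part 1 maximum) + 20 (Part 2) = 55, which matches the stated total. The 20 cannot be re-derived. SAP section 5 says it rests on clinical consideration, and there is no target rate or precision goal.

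**2. Who can be lost.** The first scheduled scan is at Week 6. Protocol 7.4 asks for an assessment when progression is suspected, so many early progressors stay in. At withdrawal, a scan is needed only if none was done in the previous 6 weeks, and the baseline scan can satisfy that. With a baseline scan L days before first dose, no exit scan is required for withdrawal up to 42 − L days after it:
- L = 1: 42 − 1 = 41 days
- L = 28: 42 − 28 = 14 days

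A note in Protocol Appendix 2 also allows a baseline assessment up to 6 weeks old; at L = 42 the gap closes.

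**3. Effect on response rate.** Let r be the number of responders and m the number of treated patients without a post-baseline assessment. Under SAP 7.1 those m cannot be responders. Keeping them gives r/20; dropping them gives r/(20 − m). The ratio is 20/(20 − m), whatever r is. The documents give neither r nor m. I assume r = 4 and m = 1 to 5, with Clopper-Pearson 95% intervals:

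| m | Factor | Rate | Exact 95% CI |
|---|---|---|---|
| 0 | 1.00 | 4/20 = 20.0% | 5.7–43.7 |
| 1 | 1.05 | 4/19 = 21.1% | 6.1–45.6 |
| 2 | 1.11 | 4/18 = 22.2% | 6.4–47.6 |
| 3 | 1.18 | 4/17 = 23.5% | 6.8–49.9 |
| 4 | 1.25 | 4/16 = 25.0% | 7.3–52.4 |
| 5 | 1.33 | 4/15 = 26.7% | 7.8–55.1 |

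**4. Long-run effect.** If a share d of treated patients is unassessed and the true rate among all treated is p, the expected estimate is p/(1 − d). For p = 20%, that is 0.20/0.90 = 22.2% at d = 10% and 0.20/0.80 = 25.0% at d = 20%. A simulation with N = 20 (200,000 runs) agreed. For p = 30%, the chance that the exact lower limit lies above the true rate was 2.2% at d = 5% and 5.8% at d = 20%, against a nominal 2.5%.

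**5. Effect on PFS.** Under SAP 7.1, living unassessed patients are censored at Cycle 1 Day 1. Only deaths before the first planned assessment make a difference. With k such deaths among the m and no other early censoring, reported S = true S × (20 − m + k)/(20 − m). For m = 5 and a true 12-week value of 50%:
- k = 0: 0.50 × 15/15 = 50%
- k = 1: 0.50 × 16/15 = 53%
- k = 2: 0.50 × 17/15 = 57%
- k = 5: 0.50 × 20/15 = 67%

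**The case against.** The strongest reply is that little depends on this rate. There is no hypothesis and no decision rule, and Part 2 was sized on clinical grounds. The largest shift shown, 6.7 points, lies inside an interval 38 points wide (43.7 − 5.7). It needs a quarter of the patients to go unassessed, although entry requires ECOG 0 or 1 and a life expectancy of at least 12 weeks. The planned listings of best response, death date and last assessment date would allow either rate to be recomputed. All of this is true, and it limits the size of the harm. It does not remove the problem. Sampling error is shown by the interval; this bias is one-sided and would not be shown.

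Several narrower points also stand:
- With no responders the point estimate does not change.
- The direction is fixed only for the 9.2.2.1 text. A Per Protocol set also removes patients with major Cycle 1 deviations, who could be responders.
- The SAP 6.2 sentence is loose and may not be a membership rule.
- A post-baseline disease assessment need not be a scan, since caliper-measured lesions qualify.
- The modified ITT wording is permissive.
- That OS falls under the 9.2.2.1 restriction is inferred from its general sentence; the table has no OS row, and SAP 7.1 assigns OS to ITT.
- The 12-week PFS value is an illustration, not a planned summary.

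None of these reconciles the passages.

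**Conclusion.** The concern holds. The protocol's Part 2 primary endpoint is secondary throughout the SAP, and Protocol 2.2 lists it as both. The denominator is defined in ways that cannot all apply, and nothing says which governs. If the SAP 9.2.2.1 text is followed, the response rate is biased upward relative to all treated patients with baseline disease whenever there is at least one responder and at least one unassessed patient. The inflation is 5% to 33% in relative terms for an assumed 1 to 5 unassessed of 20, or about 1 to 7 percentage points with an assumed 4 responders. It is zero if every patient is assessed. PFS is affected less. Type I error and power are not at issue, because nothing is tested. The correction belongs in place before Part 2 is analysed.

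**What to change.** - **Status.** In SAP 7.1, 9.2.1 and 9.2.2.1, name confirmed response rate as the Part 2 primary endpoint, and limit the DLT statement in SAP 7.2.1 to Part 1. Reconcile the duplicate secondary entry in Protocol 2.2, and the Protocol 9.4 wording that makes the response summary conditional on the data.
- **Denominator.** Use all dosed Part 2 patients with a baseline assessment and measurable disease (Protocol 9.4.1). Count patients without a post-baseline assessment as non-responders (SAP 7.1), with an exact 95% interval.
- **SAP 9.2.2.1.** Delete the post-baseline condition. In the response row of the table, enter this set in place of the open-ended one, and non-responder in place of censoring. Align the Per Protocol sentence in SAP 6.2 and Protocol 9.1.
- **PFS and OS.** For PFS use all treated Part 2 patients, with deaths before the first planned assessment as events. Align OS with its ITT definition, and say how patients who were never dosed are handled, since OS is timed from first dose.
- **Confirmation window.** Reconcile the Schedule of Activities and Protocol 7.4, which put the confirming assessment at most 4 weeks after first response, with Protocol 9.4.1 and SAP 7.1, which put it at least 4 weeks after.
- **Reporting.** Give m, and show the assessed-only rate as a labelled sensitivity analysis.

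The cost is wording in both documents. The denominator change adds no patients, visits or scans; the reported rate may be slightly less favourable. Any scan cost of the confirmation window depends on how it is reconciled and is not assessed here.

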### **6.2. ‘PER PROTOCOL’ Analysis Set**

*The per protocol analysis set includes all enrolled patients who receive at least one dose of study medication at the dose level of RP2D and who do not have major treatment deviations during first cycle. Patients with major treatment deviations in Cycle 1 are not evaluable for the RP2D assessment. Major deviations include failure to satisfy major entry criteria (eg, confirmation of the target disease; signed informed consent) or use of other anticancer treatments during the active treatment and disease follow-up phases other than as defined/allowed in this protocol. A baseline disease assessment and at least one post-baseline disease assessment are appropriate to allow efficacy analysis.*

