## 6.8. Protocol Deviations

All deviations will be listed in the CSR. Major treatment deviations include, but are not limited to, less than 80% of the planned Cycle 1 PF-06650808 dose provided the reduction/omission is not due to treatment-related toxicity. Subjects with major Cycle 1 treatment deviations are not evaluable for MTD.

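### SAP 9.2.2.1 gives two different patient sets for Part 2 efficacy, and its text leaves out treated patients with no post-baseline assessment, whom Protocol 9.4.1 keeps

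*SAP*

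**What the plan says.** Protocol 9.4.1 sets the rule for who is evaluable for efficacy: "they must have received at least one dose of study medication and have a baseline tumor assessment". Measurable disease is the only further condition. Nothing after baseline is required.

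SAP 9.2.2.1 then describes the population twice.

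- Text: patients in the MTD expansion cohorts "who are in the Safety Analysis Set and have baseline disease assessment and at least one post-baseline disease assessment".
- Overview table: "Per Protocol, expansion cohorts, etc" in the overall response row, and Per Protocol in the expansion cohorts for PFS, time to progression (TTP) and duration of response (DR). All four rows are labelled as secondary analyses. OS is named in the text but has no row.

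SAP 6.2 limits Per Protocol to patients "who do not have major treatment deviations during first cycle". It adds: "A baseline disease assessment and at least one post-baseline disease assessment are appropriate to allow efficacy analysis". Its examples of major deviations include "use of other anticancer treatments during the active treatment and disease follow-up phases" where the protocol does not allow it. SAP 6.8 goes further: "Major treatment deviations include, but are not limited to, less than 80% of the planned Cycle 1 PF-06650808 dose", unless treatment-related toxicity was the cause.

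SAP 7.1 lists who does not count as a responder. The list opens with "Patients who do not have on-study radiographic tumor re-evaluation, who receive anti-tumor treatment other than the study medication"; the second group applies when that treatment comes before a response. For PFS, SAP 7.1 and Table 3 in Appendix 3 count a death before the first planned assessment as an event. SAP 7.1 measures OS in the intent-to-treat population.

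**The concern.** The text and the table of one SAP section name different sets, and neither is marked as the main one. The 'etc.' in the response row leaves that set open-ended. The study is open-label, so the choice of denominator could be made after the responses are known.

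The text's requirement of an assessment after baseline also conflicts with rules elsewhere in the plan. Protocol 9.4.1 does not impose it. The SAP 7.1 rule on patients without radiographic re-evaluation is most naturally read as placing them in the denominator as non-responders, and it has little to do if they have already been removed. The same applies to the PFS rule on early deaths.

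At stake is the Part 2 estimate itself. The SAP plans no hypothesis test and puts its emphasis on estimation, so the response rate and its interval are the efficacy result.

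**Working it through.** The plan gives no target rate, power or precision for Part 2, so there is no stated figure to reproduce. The check is a comparison of definitions, followed by an illustration.

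**1. Who is in each set** (treated Part 2 patients with a baseline assessment and measurable disease; Part 2 inclusion criterion 2 already requires a measurable lesion)

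| Patient | Protocol 9.4.1 | SAP 9.2.2.1 text | SAP 9.2.2.1 table (Per Protocol) |
|---|---|---|---|
| Assessed after baseline, no deviation | in | in | in |
| Not assessed after baseline | in | out | out on the natural reading of SAP 6.2, though the wording is soft |
| Major Cycle 1 treatment deviation, assessed after baseline | in | in | out |

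Three rules can therefore give three denominators. A patient given another anticancer treatment in Cycle 1 shows the clash: removed under Per Protocol, but a non-responder under SAP 7.1.

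**2. Can a patient go unscanned without a protocol deviation?** Note 17 of the Schedule of Activities puts the first scan at Week 6, ends scanning at permanent discontinuation, and asks for an End of Treatment scan only when more than 6 weeks (42 days) have passed since the last one. The baseline scan may be up to 28 days before Day 1. With the earliest baseline scan, 42 − 28 = 14, so a patient who stops by about Day 14 needs no further scan under that note. With a baseline scan just before Day 1, this holds until the Week 6 scan is due. Protocol 7.4 adds a scan when progression is suspected, which leaves mainly early deaths and early withdrawals for other reasons.

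**3. Effect on the response rate.** SAP 9.1 specifies an exact two-sided 95% interval, taken here as Clopper-Pearson. For r responders out of n, the lower limit is the 0.025 quantile of Beta(r, n − r + 1) and the upper limit is the 0.975 quantile of Beta(r + 1, n − r). Planned n is about 20. The values of r and of m, the number unscanned, are assumptions. An unscanned patient is not a responder under SAP 7.1, so leaving out m patients multiplies the rate by 20/(20 − m).

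| r | m | Rate | Exact 95% CI |
|---|---|---|---|
| 4 | 0 | 4/20 = 20.0% | 5.7 to 43.7 |
| 4 | 1 | 4/19 = 21.1% | 6.1 to 45.6 |
| 4 | 2 | 4/18 = 22.2% | 6.4 to 47.6 |
| 4 | 4 | 4/16 = 25.0% | 7.3 to 52.4 |
| 2 | 0 | 2/20 = 10.0% | 1.2 to 31.7 |
| 2 | 2 | 2/18 = 11.1% | 1.4 to 34.7 |
| 6 | 0 | 6/20 = 30.0% | 11.9 to 54.3 |
| 6 | 2 | 6/18 = 33.3% | 13.3 to 59.0 |

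The m = 4 row shows the range; nothing in the documents suggests so many.

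**4. Effect of also removing Cycle 1 deviators.** With 2 unscanned and 2 deviators (assumed), n = 20 − 2 − 2 = 16. The rate is 4/16 = 25.0% if neither deviator responded and 3/16 = 18.8% (4.0 to 45.6) if one did. This exclusion can move the rate either way.

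**5. Effect on PFS.** Assume 8 of 20 are event-free at Week 12, no other censoring, and 2 deaths before the first planned assessment with no earlier unscheduled scan. Keeping the deaths gives 8/20 = 40.0%; removing them gives 8/18 = 44.4%.

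**The case against.** The text of SAP 9.2.2.1 is directive and the table only offers an overview, so the text could be taken to govern. That would settle which set is used. It would also settle on the set with the explicit exclusion, so the conflict with Protocol 9.4.1 would remain.

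Unscanned patients should be uncommon. Besides the Protocol 7.4 scan on suspected progression, Appendix 2 urges documentation of progression after treatment stops, and entry requires ECOG 0 or 1 and a life expectancy of at least 12 weeks. Cycle 1 is a single infusion of about 60 minutes, so non-toxicity dosing below 80% should also be rare. These points stand and limit the size of the effect, but not its direction for unscanned patients.

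SAP 7.1 states no denominator, and it speaks of radiographic re-evaluation where SAP 9.2.2.1 asks for a disease assessment. A patient with only a caliper measurement could meet the second and not the first, so the two rules can partly coexist. This stands, but it does not help a patient with no assessment of any kind.

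Living unscanned patients are censored at C1D1 and add nothing to the Kaplan-Meier curve, so for PFS only early deaths matter. The efficacy listings would let a reader recompute other rates. The mITT set in SAP 6.6.1 keeps early progression and death, but it is described for occasions such as presentations while the study is ongoing, not for the final analysis.

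**Conclusion.** The point holds. SAP 9.2.2.1 names two sets that differ by the Cycle 1 deviators. The set in its text leaves out treated patients whom Protocol 9.4.1 keeps, and SAP 6.2 points the same way in softer words. Protocol 2.2 makes response rate primary for Part 2, although the SAP labels all efficacy as secondary. The bias from unscanned patients is upward whenever there is at least one responder. It is about 2 percentage points with 4 responders and 2 unscanned of 20, against intervals that are wide either way. All patient counts are assumed, and the reading of SAP 7.1 as a denominator rule is the natural one rather than an explicit one. No formal decision depends on the result.

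Three stronger readings are tempting but not supported.

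- A reader might infer that the text's set can hold no patient who dies before the first planned assessment. It can: an unscheduled scan for suspected progression would qualify such a patient. Only early deaths without any such assessment are lost.
- A reader might infer that SAP 6.2 expressly bars unscanned patients from Per Protocol. It says only that the assessments are appropriate for efficacy analysis.
- A reader might infer that Per Protocol misses Part 2 patients altogether, because it requires a dose at the RP2D while Part 2 enrols at the MTD. The documents mostly treat the two as one dose. Protocol 3.4, and the provision in Protocol 3.1 for later changes to the recommended dose, leave room for a difference, but the problem would arise only if the doses came to differ.

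**What to change.** Change SAP 9.2.2.1 only, with text and table made to agree.

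1. Main set for Part 2 response: all treated Part 2 patients with a baseline tumor assessment and measurable disease, as in Protocol 9.4.1. Count patients with no post-baseline scan as non-responders.
2. PFS: all treated Part 2 patients under the Table 3 rules, so that deaths before the first planned assessment stay in as events.
3. OS: state that it follows SAP 7.1 and uses the intent-to-treat population.
4. Label Per Protocol as supportive and delete 'etc.' from the response row.

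The cost is SAP wording, with no additional patients, visits or data and no protocol amendment. The downside is that the reported response rate may be slightly lower.

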### 11.3. APPENDIX 3: CENSORING DETAILS

**Table 3. Progression Free Survival and Duration of Response**

Situation	Date of Progression/Censoring 	Outcome
Inadequate baseline assessment	Start date (C1D1)	Censored
No on-study assessments	Start date (C1D1)	Censored
Alive, on treatment  and no Progression	Date of last objective tumor assessment	Censored
Progression Documented on or between scheduled tumor assessments prior to treatment discontinuation 	Date of first objective tumor assessment showing objective progression	Progressed (Event)
Treatment discontinuation for undocumented progression	Date of last objective tumor assessment prior to discontinuation 	Censored
Treatment discontinuation due to toxicity or other reason	Date of last objective tumor assessment prior to discontinuation 	Censored
Death prior to first planned tumor assessment	Date of death	Death (Event)
Death without objective progression prior to treatment discontinuation 	Date of death	Death (Event)
Death or progression after 2 or more missed tumor assessments	Date of last objective tumor assessment prior to the event	Censored

1: For date of censorship, if a tumor assessment takes place over a number of days (eg, superficial lesions one day, scans another), the last date is used as the assessment date.

2: or within 28 days of discontinuation of treatment.

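### The SAP efficacy table assigns overall response a time-to-event censoring rule, which leaves the denominator of the Part 2 response rate undefined

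*SAP*

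**What the plan says.** The table in SAP 9.2.2.1 has one row per efficacy endpoint. For Overall response the Analysis Set cell reads "Per Protocol, expansion cohorts, etc", the method is an exact confidence interval, and the Missing Data cell, further along the same row, sends the reader to the censoring rules in Section 11.3. The three Kaplan-Meier rows (PFS, time to progression, duration of response) carry the same Missing Data entry.

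Section 11.3 (Appendix 3) holds two tables: "Table 3. Progression Free Survival and Duration of Response", and a second one for time to progression. SAP 8.2 states its scope: "Censoring rules for time-to-event endpoints are detailed in" that appendix. One of the situations that Table 3 censors is "Treatment discontinuation due to toxicity or other reason".

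The only rule written for response is in SAP 7.1. "Patients who do not have on-study radiographic tumor re-evaluation", and those "who die, progress, or drop out for any reason prior to reaching a CR or PR will not" be counted as responders.

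The text above the table limits the efficacy analysis to expansion patients "who are in the Safety Analysis Set and have baseline disease assessment and at least one post-baseline disease assessment". Protocol 9.4.1 asks for less: at least one dose, a baseline tumour assessment and measurable disease.

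**The concern.** A response rate with an exact interval has a numerator and a denominator and nothing else. Each patient is a responder, a non-responder, or not in the set. A censoring instruction cannot be carried out for such an endpoint, and the section it cites contains no line on response. Whoever programs the table must choose between ignoring the cell and reading it as permission to leave patients out.

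The protocol (2.2) makes response rate the primary endpoint of Part 2, with about 20 patients, so each exclusion moves the estimate visibly. The missing-data rule for that endpoint should be usable as written and should agree with the endpoint definition.

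**Working it through.** **Inputs.** Part 2 has about 20 patients (protocol 9.3, SAP 5), which fits the planned total: 35 + 20 = 55. Binary endpoints get exact two-sided 95% intervals (SAP 9.1). The documents give no expected response rate, dropout rate or interval width, so there is no figure of the plan's own to reproduce for this endpoint. The responder and exclusion counts below are assumptions.

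**Step 1: the rules side by side.**

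| Patient | SAP 11.3, Table 3 (PFS, DR) | SAP 7.1 (response) |
|---|---|---|
| No on-study assessment | Censored at C1D1 | Not a responder |
| Stops for toxicity or another reason before CR/PR | Censored at last assessment | Not a responder |
| Stops for undocumented progression before CR/PR | Censored at last assessment | Not a responder |
| Dies before first planned assessment | Event | Not a responder |
| Alive, on treatment, not progressed | Censored at last assessment | Responder if CR/PR is confirmed |

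Section 11.3 classifies follow-up time and does not say who counts in a proportion. The last row matters for direction: Table 3 censors without regard to response, so the patients it censors can include responders.

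**Step 2: the sentence above the table.** A patient with no post-baseline assessment is outside the efficacy population of SAP 9.2.2.1. The first clause of the SAP 7.1 rule, on patients without radiographic re-evaluation, then has almost nobody to act on. Protocol 9.4.1 would keep such patients in. This sentence is the explicit route out of the denominator; the Missing Data cell only leaves a route open.

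**Step 3: illustration, only non-responders left out.** With x responders among 20 and m non-responders omitted, the rate is x/(20 − m), which is the full-denominator rate multiplied by 20/(20 − m). For x = 4, with Clopper-Pearson limits:

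| m | Rate | Exact 95% CI | Factor |
|---|---|---|---|
| 0 | 4/20 = 20.0% | 5.7 to 43.7% | 1.00 |
| 2 | 4/18 = 22.2% | 6.4 to 47.6% | 1.11 |
| 4 | 4/16 = 25.0% | 7.3 to 52.4% | 1.25 |
| 6 | 4/14 = 28.6% | 8.4 to 58.1% | 1.43 |

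For x from 2 to 6 and m = 4, the rate moves from 10.0–30.0% to 12.5–37.5%, and the upper limit from 31.7–54.3% to 38.3–64.6%.

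**Step 4: illustration, responders also left out.** If k patients are removed, r of them responders, the rate is (x − r)/(20 − k). This is below x/20 whenever r/k exceeds x/20. With x = 4, k = 6 and r = 2, r/k = 33% exceeds 20%, and the rate is 2/14 = 14.3% (1.8 to 42.8%). The error can go either way.

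**The case against.** The best defence is that the cell is a carried-over cross-reference with no practical effect. The table is offered as an overview, all four rows carry the same entry, and Section 11.3 is silent on response, so the explicit rule in SAP 7.1 governs. Patients who were scanned and later stopped also have no missing response: Table 2 in SAP Appendix 2 gives them a best overall response even when the next time point is not evaluable. The study tests no hypothesis (SAP 4.1), and listings by patient would let a reader recompute the rate.

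Much of this stands. A reader might infer that the SAP instructs the analyst to drop early discontinuers. It does not; exclusion is one way of acting on an unusable entry. A reader might also infer that the response rate is biased upward by 11% to 43%. The documents do not support that either: Table 3 censors regardless of response, and the counts are assumed. SAP 7.1 itself says who is not a responder without stating the denominator.

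The defence does not make the cell correct. A missing-data entry for a protocol primary endpoint that has to be ignored to reach the right answer should be replaced. The post-baseline condition above the table is also a written restriction, not an inference.

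**Conclusion.** The Missing Data entry for overall response is wrong for a binary endpoint. It cites a section that SAP 8.2 reserves for time-to-event endpoints and passes over the non-responder rule in SAP 7.1. The result is an open denominator for the Part 2 response rate, not a demonstrated bias. The movement from 20% to 22–29% holds only if 4 of 20 respond and 2 to 6 patients, all non-responders, are left out. Removing responders as well could lower the rate. The correction is worth making because the protocol names this endpoint as primary for Part 2. That the SAP calls all efficacy endpoints secondary is a separate matter, and this point does not depend on it.

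**What to change.** Two changes to SAP 9.2.2.1:

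1. In the Overall response row, replace the Missing Data entry with: *Counted as non-responder per Section 7.1; no patient in the analysis set is removed from the denominator.* Keep the reference to Section 11.3 for PFS, time to progression and duration of response only.
2. For the response rate, align the sentence above the table with protocol 9.4.1 (at least one dose, baseline tumour assessment, measurable disease), so that patients without re-evaluation stay in the denominator as non-responders. The per protocol definitions in SAP 6.2 and protocol 9.1 carry a similar remark about a post-baseline assessment, so the text should say that this remark does not restrict the response denominator.

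The first change alone would leave the post-baseline condition in force. Together they cost one table cell and a short text edit, with no new data, patients or analyses. The downside is that the reported rate may be slightly lower.
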